4.5 Endpoints

4.5.1 **Primary Endpoint**

The primary endpoint of this study is safety-related and is the occurrence of DLTs during the study.

Protocol Number: NVGN-0084-201

Secondary Endpoints 4.5.2

Secondary endpoints are related to both, safety and clinical benefit as listed below.

Secondary Safety Endpoints:

- Treatment-emergent AEs (TEAEs), Grade 3-5 TEAEs, serious adverse events (SAEs), fatal AEs, and TEAEs leading to GDC 0084 discontinuation or study withdrawal;
- Treatment-emergent Grade 3/4 clinical laboratory abnormalities;
- Changes and shifts from baseline in clinical laboratory, vital signs, and ECG parameters;
- Change from baseline in corticosteroid use;
- Change from baseline in LVEF;
- Change from baseline in KPS;
- Concomitant medication use;
- Adherence to the dosing regimen.

Secondary Endpoints of Clinical Benefit:

- PFS measured from first dose in the dose-escalation portion (Stage 1) or from randomization in the cohort expansion portion of the study (Stage 2) to disease progression (RANO criteria) or death due to any cause:
- OS measured from first dose in the dose-escalation portion (Stage 1) or from randomization in the cohort expansion portion of the study (Stage 2) to death due to any cause;
- TTP measured from first dose in the dose-escalation portion (Stage 1) or from randomization in the cohort expansion portion of the study (Stage 2) to date of earliest disease progression according to RANO criteria.

4.5.3 **Exploratory Endpoints**

Exploratory endpoints in this study are:

- PFS measured from first dose in the dose-escalation portion (Stage 1) or from randomization in the cohort expansion portion of the study (Stage 2) to disease progression (modified RANO criteria) or death due to any cause:
- PK parameters including area under the curve from time 0 to last measurable time point (AUC_{0-last}) and/or area under the curve from time 0 to infinity (AUC_{0-inf}), maximum concentration (C_{max}), minimum concentration (C_{min}), time to reach C_{max} (T_{max}), t_{1/2}, apparent total clearance of the drug from plasma after oral administration (CL/F), and accumulation ratio for C_{max} and AUC (fed and fasted);
- Change in FDG-PET uptake in tumor and normal brain tissue (defined as normal brain tissue with similar cell type to tissue surrounding tumor) in response to GDC-0084 in patients with measurable disease:
- DCR measured as the proportion of patients achieving a confirmed best overall response (BOR) of complete response (CR), partial response (PR), or stable disease (SD) according to a) RANO criteria and b) modified RANO criteria.

Assessments

All assessments outlined in this section will be performed in accordance with the Schedule of Assessments (see Table 1).

4.6.1 Physical and Ophthalmologic Examination

The physical examination will include an evaluation of body systems (e.g. cardiovascular, gastrointestinal, neurological, head and neck, respiratory, dermatology). Evaluation for pre-existing

Version: Amendment 4

IND Number: 112.608 Date: 31 Mar 2020

conditions that might exclude the patient from eligibility or could interfere with the patient's participation and compliance with the protocol should be performed at Screening.

The ophthalmologic examination should include use of a slit-lamp or similar equipment to assess corneal opacity.

Protocol Number: NVGN-0084-201

Height, Weight and Vital Signs 4.6.2

Body height (at screening only), weight, and vital signs (blood pressure, pulse and temperature) will be measured.

4.6.3 Radiographic Assessments

For all patients, an MRI of the brain will be performed; cranial MRI scan must have been performed within 14 days prior to or on the day of the Enrollment/Week 1 visit and then every 8 weeks starting at Week 8. The international standardized brain tumor imaging protocol will be followed for MRI imaging. Minimum sequences required are: 3D pre-contrast T1, T2/FLAIR, and 3D post-contrast T1. Slice thickness for 3D pre- and post-contrast T1 images should be ≤ 1.5 mm with no gap and slice thickness for 2D T2 and FLAIR should be ≤ 4 mm with no interslice gap.

For the expansion cohort, the assessment of disease progression will be done by MRI analysis according to RANO criteria. Evaluation will be conducted by a central radiography vendor using 2 central readers who are blind to treatment assignment (fed or fasted), with an adjudication process when there is disagreement between the 2 central readers.

Patients in Stage 2 with measurable disease, and subject to research site having capability, will be required to undergo FDG-PET imaging and analyses will be performed by accredited specialist facilities.

FDG-PET imaging will occur at Randomization/Week 1, Days 3 and 7 of Cycle 1. Timing and days of FDG-PET imaging may change on the basis of PK e.g. T_{max} and other data analyzed during the study. FDG-PET imaging may be obtained using a stand-alone PET or combined PET/computed tomography (CT) scanner, or hybrid PET/MRI systems.

The image acquisition system must remain consistent throughout all scans for the same patient. MRI imaging will be performed according to standardized procedures. The central review disease response assessments will be used as the primary measure for analysis, and the Investigator disease response assessments will be used as supportive measures for analysis.

At the Randomization/Week 1 visit, the baseline pre-treatment FDG-PET imaging must be performed prior to the pre-dose PK sample and the first intake of GDC-0084. Imaging should be completed at least 1 hour prior to pre-dose PK sampling. For logistical reasons, the pre-treatment FDG-PET may be performed up to 1 day prior to the Randomization/Week 1 visit.

Prior to the scheduled FDG injection, patients should fast for at least 4 hours (preferably 6 hours). The blood glucose level should be determined at the time of the FDG-PET scan. Use of anti-hyperglycemic medications, including insulin, immediately prior to the FDG-PET scan is not permitted, as these agents will impact FDG uptake and compromise the interpretability of the FDG-PET scan. Specifically, no short-acting insulin should be administered within 4 hours prior to FDG administration.

Median and mean FDG-PET standard uptake value within the contrast enhancing, measurable target lesion(s), contralateral normal-appearing cortical tissue, and contralateral normal-appearing white matter will be quantified.

4.6.4 **Cardiac Assessment**

Cardiac assessment will be performed by the Investigator and be based on assessment of medical history, physical examination, 12-lead ECG results (including QTc) and evaluation of LVEF by echocardiography (ECHO) or multi-gated scan (MUGA) as well as, as clinically indicated, measurement of troponin T and B-type natriuretic peptide as potential biomarkers of early

Version: Amendment 4 Date: 31 Mar 2020

cardiotoxicity. Cardiology consult may be sought by the Investigator if required to confirm suitability for inclusion in the study.

Protocol Number: NVGN-0084-201

IND Number: 112.608

Except for baseline ECGs at screening, ECGs should be conducted approximately 2 hours post-dose, to coincide with the approximate timing of T_{max} determined in a prior clinical study.

4.6.5 Karnofsky Performance Status

The KPS will be determined using the criteria defined in the Appendix.

4.6.6 O₆ Methylguanine-Methyltransferase Promoter Status

The unmethylated MGMT promoter status will be confirmed by validated PCR or alternate validated technique, according to standard practice at each site.

4.6.7 Pharmacokinetic Assessments

Pre- and post-dose plasma samples will be collected for PK analysis. All doses of GDC-0084 used for PK evaluations are to be administered in the clinic and are to be given with 240 mL of water. In Stage 1, patients should fast for 10 hours pre-dose and for 4 hour post-dose on days when they undergo PK assessments. In Stage 2, those subjects allocated to the fasted arm should fast for 10 hours pre-dose and for 4 hours post-dose on days when they undergo PK assessments. Those subjects allocated to the fed arm should consume a high-fat, high-calorie meal approximately 30 minutes prior to dosing, and should fast thereafter for at least 4 hours. All patients should be consistently seated or standing for the first 4 hours post dose on PK days, except when ECG recordings are made.

Stage 1

On Day 1 of Cycle 1, plasma samples for PK analysis will be collected at least 15 minutes prior to the visit dose, and then at 30 (+/- 3) minutes, and at 1 (+/- 10 minutes), 2 (+/- 15 minutes), 3 (+/- 15 minutes), 4 (+/- 15 minutes), 6 (+/- 15 minutes), 8 (+/- 15 minutes) and 24 (+/- 1) hours post dose. The 24- hour sample should be obtained at least 15 minutes prior to administration of the following day's dose. On Day 1 of Cycle 2, plasma samples for PK analysis will be collected at least 15 minutes prior to administration of GDC-0084. The site should also record the time that the Day 28 dose was taken based on patient information and/or diary card.

Stage 2

On Day 1 of Cycle 1, an appropriate plasma sample for PK analysis will be collected at least 15 minutes prior to the visit dose, and then at 30 (+/- 3) minutes, and at 1 (+/- 10 minutes), 2 (+/- 15 minutes), 3 (+/- 15 minutes), 4 (+/- 15 minutes), 6 (+/- 15 minutes), 8 (+/- 15 minutes) and 24 (+/- 1 hour). The 24-hour sample should be obtained at least 15 minutes prior to administration of the following day's dose. On Day 1 of Cycle 2, an appropriate plasma sample for PK analysis will be collected at least 15 minutes prior to the visit dose. The site should also record the time that the Day 28 dose was taken based on patient information and/or diary card.

All samples for concentrations of GDC-0084 will be analyzed by a central laboratory. Samples should be collected in accordance with the procedures specified by the central laboratory and detailed in the Laboratory Manual.

4.6.8 Safety Laboratory Assessments

Blood samples of approximately 10 mL per assessment of hematological and serum chemistry parameters will be collected and processed in accordance with the laboratory procedures.

All hematology and serum chemistry samples will be submitted by the Investigator to the certified laboratory for analysis. Blood samples for hematology and serum chemistry will be prepared using standard procedures. Laboratory results should be reviewed by the Principal Investigator or another qualified study staff member as soon as received.

Safety laboratory panels are defined as follows:

Protocol Number: NVGN-0084-201 Version: Amendment 4 IND Number: 112.608 Date: 31 Mar 2020

Hematology and Coagulation: red blood cell count (RBC), hemoglobin, hematocrit, reticulocyte count, WBC with differential (neutrophils, bands, eosinophils, basophils, lymphocytes, monocytes, and other cells), platelet count aPTT, PT, and INR;

Serum chemistry: blood urea nitrogen (BUN) or urea, creatinine, sodium, chloride, potassium, magnesium, bicarbonate, calcium, phosphorus, total protein, albumin, alkaline phosphatase, fasting glucose, total bilirubin, direct and indirect bilirubin, lactate dehydrogenase (LDH), cholesterol, uric acid, triglyceride levels, gamma glutamyl transferase (GGT), AST, and ALT.

Abnormalities in clinical laboratory tests that are considered clinically significant by the Investigator will be recorded on the laboratory Case Report Form (CRF) page. If abnormal laboratory results are also considered an AE, then a corresponding AE CRF will also be completed. If values after the first dose meet criteria defining them as serious, they must be reported as SAEs.

Unscheduled and repeat laboratory tests may be performed by the laboratory to allow a short as possible turnaround time for rapid clinical management of the patient, if necessary. A Laboratory Manual with instructions on specimen collection, processing, storing, and shipping will be in place for all participating sites.

4.6.9 **Pregnancy Test**

For female patients of childbearing potential, a serum pregnancy test, will be performed immediately before administration of first dose of the investigational product. At subsequent visits, a negative pregnancy urine test result is required before the patient may receive the investigational product. If the urine pregnancy test is positive, then confirmation of pregnancy will be by bHCG blood test. If bHCG blood test is negative, then administration schedule may resume. Pregnancy tests may also be repeated as per request of the IRB or if required by local regulations.

4.6.10 Adverse Events

The assessment of AEs will be performed throughout the study, according to the criteria and procedures outlined in Section 5.

4.6.11 Unscheduled Visits

Unscheduled visits may be conducted at any time during the study by the Investigator if clinically indicated for the care of the patient. An unscheduled visit may include any of the protocol required assessments listed in Section 4.6. The exact assessments conducted at the unscheduled visit will be specified by the Investigator and recorded in the CRF. Additional tests and procedures may be performed at the unscheduled visit for the clinical care of the patient after discussion with, and agreement of, the medical monitor.

4.6.12 Follow-up Visits

There is a short-term follow-up visit 28 days after end of study treatment (last dose). There is longterm follow-up performed by telephone conversation or site visit (depending on practical considerations) where all patients in Stage 1 and Stage 2 who discontinue study treatment will be followed every 8 weeks until determination of progressive disease (PD) and then until death unless the patient requests to be withdrawn from survival follow-up or termination of the study by the Sponsor. This request must be documented in the source documents and signed by the Investigator.

Duration of Therapy

After the screening period of up to 28 days, patients start to take GDC-0084 in 28-day cycles (every day continuous dosing is intent). Dose and regimen depend on the study stage and findings during the study (see Section 3.7 and Section 4.4.1).

In the absence of treatment delays due to AEs, treatment may continue until 1 of the following criteria applies:

- DLTs (Stage 1, Cycle 1);
- Disease progression;
- Intercurrent illness that prevents further administration of treatment:

Version: Amendment 4 Date: 31 Mar 2020

IND Number: 112.608

- Patient decides to withdraw from the study;
- General or specific changes in the patient's condition that render the patient unacceptable for further treatment in the judgment of the Investigator.

Protocol Number: NVGN-0084-201

4.8 Duration of Follow-up

There is a short-term follow-up visit 28 days after end of study treatment. There is long-term follow-up performed by telephone conversation or site visit (depending on practical considerations) where all patients in Stage 1 and Stage 2 who discontinue study treatment will be followed every 8 weeks until determination of progressive disease (PD) and then until death unless the patient requests to be withdrawn from survival follow-up or termination of the study by the Sponsor. This request must be documented in the source documents and signed by the Investigator. PD and death will be reported as part of the study endpoints and not as AEs or SAEs.

4.8.1 Schedule of Assessments in Follow-up

Procedures during follow-up will be performed according to the Schedule of Assessments (Table 1).

4.9 Dose Delays and Dose Modifications

4.9.1 **Retreatment Criteria**

Prior to proceeding to the next cycle, patients must have recovered the following organ function:

- Absolute neutrophil count $\geq 1.5 \times 10^9 / L$;
- Platelets $\geq 100 \times 10^9 / L$;
- Total bilirubin within normal institutional limits;
- AST/ALT ≤ 2.5 X institutional ULN.

Laboratory evaluations must be performed within 48 hours prior to initiation of each cycle of therapy. Patients not fulfilling these criteria should have treatment delayed until the recovery of organ function. Patients who cannot be retreated within 2 weeks of the end of the previous cycle should be removed from study.

4.9.2 **Dose Modification Guidelines**

In general, dose modifications are not foreseen during the study. However, under certain circumstances in which the risk/benefit assessment suggests a reasonable rationale for continued treatment with GDC-0084, e.g., after an AE (or DLT), patients may continue with a reduced dose or a change of treatment schedule if the Investigator and medical monitor agree.

Patients in Stage 1 will be enrolled to their allocated dose at a QD dosing frequency. They will continue to receive study drug based on the cohort to which they are assigned, and intra-patient dose escalation is not permitted. Dose reduction is permitted if clinically indicated.

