- Grade ≥ 3 non-hematologic or non-hepatic toxicity that is not related to hyperglycemia or hyperlipidemia or mucositis/stomatitis and is not due to disease progression or another clearly identifiable cause, excluding the following:
 - Alopecia of any grade;
 - Grade 3 fever or Grade 4 fever < 5 days duration;
 - Grade 3 infection < 5 days duration or that responds to treatment;
 - Grade 3 weight gain or loss;
 - Grade 3 diarrhea lasting less than 5 days or that responds to standard-of-care therapy including hospitalization;
 - Grade 3 nausea or vomiting, in the absence of premedication, that lasts for less than 48 hours or responds to standard-of-care therapy:
 - Grade 3 or asymptomatic Grade 4 electrolyte imbalance that resolves or improves within 7 days with or without medical intervention, including hospitalization;
 - Grade 3 or 4 serum amylase or lipase or creatine phosphokinase laboratory abnormality that is asymptomatic (without other laboratory evidence suggestive of pancreatitis, rhabdomyolysis, or other major organ dysfunction) and returns to baseline within 7 days of interrupting study drug;

Version: Amendment 4 Date: 31 Mar 2020

Protocol Number: NVGN-0084-201 IND Number: 112.608

o Grade ≥ 3 total bilirubin or hepatic transaminase (aspartate aminotransferase [AST] and alanine aminotransferase [ALT]) elevations that return to ≤ Grade 1 (if normal at study entry) or ≤ baseline values within 7 days of interrupting study drug:

- Note: Allergic reactions that necessitate discontinuation of study drug will not be considered a DLT:
- Grade ≥ 3 symptomatic fasting hyperglycemia (e.g., dehydration or acidosis requiring hospitalization):
- Grade ≥ 4 fasting hypercholesterolemia or triglyceridemia for ≥ 14 days despite intervention with a lipid-lowering agent;
- Grade ≥ 4 thrombocytopenia;
- Grade 3 thrombocytopenia that lasts ≥ 7 days or is associated with clinically significant
- Grade ≥ 4 neutropenia (absolute neutrophil count < 500/µL) lasting ≥ 7 days or accompanied by fever (oral or tympanic temperature ≥ 38.0°C [100°F]);
- Grade ≥ 3 total bilirubin or hepatic transaminase (ALT or AST) elevations that do not return to ≤ Grade 1 (if normal at study entry) or ≤ baseline values within 7 days of interrupting study drug:
- For patients with Gilbert's disease and with Grade 2 bilirubin at baseline, total bilirubin ≥ 10 x upper limit of normal (ULN) will be considered a DLT;
- Bradycardia Grade ≥ 2;
- Myocardial ischemia Grade ≥ 2;

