4.2 Eligibility Criteria

4.2.1 **Inclusion Criteria**

Patients must meet all the following inclusion criteria to be eligible for enrollment into the study:

- 1) Signed informed consent approved by the Institutional Review Board (IRB). Patients must sign an authorization for the release of their protected health information;
- 2) Age ≥ 18 years;
- 3) Life expectancy > 12 weeks;
- 4) Present with histologically confirmed intracranial (supratentorial) unmethylated MGMT promotor status GBM (WHO Grade IV astrocytoma) with an MGMT status that has been confirmed by validated PCR or validated alternative genomic analysis;
- 5) Have undergone maximal or subtotal surgical resection of their tumor and within 6 weeks of surgery commenced radiation and then received at least 75% of planned treatment with XRT/TMZ or XRT only (if clinically indicated), which consists of XRT by external beam to a partial brain field in daily fractions of 2.0 Gray (Gy), to a planned total dose to the tumor of 60.0 Gy, in conjunction with TMZ oral QD 75 mg/m² in accordance with the Stupp regimen;
- 6) Karnofsky Performance Status (KPS) ≥ 70;
- 7) Cranial magnetic resonance imaging (MRI) must have been performed within 14 days prior to or on the day of the Enrollment/Week 1 Visit;
- 8) Stable or decreasing corticosteroid dose within 7 days prior to the first dose;
- 9) Adequate bone marrow/hematological function within 14 days prior to Day 1:
 - White blood cell count (WBC) > 3,000/µL, absolute neutrophil count > 1,500/mm³;
 - Platelet count of > 100,000/mm³;
 - Hemoglobin > 10 mg/dL;
 - Eligibility level for hemoglobin may be reached by transfusion;
- 10) Adequate liver function within 14 days prior to Day 1:
 - Total bilirubin ≤ 1.5 x ULN;
 - AST and ALT ≤ 2.5 x ULN;
- 11) Adequate renal function within 14 days prior to Enrollment/Week 1 Visit:
 - Creatinine ≤ 1.5 mg/dL;
 - Urine dipstick for proteinuria < 2+. Patients discovered to have ≥ 2+ proteinuria on dipstick urinalysis should undergo a 24-hour urine collection and must demonstrate ≤ 1.0 g of protein in 24 hours: OR
 - Urine protein/creatinine ratio ≤ 1.0;
- 12) International normalized ratio (INR) or prothrombin time (PT) (secs) and activated partial thromboplastin time (aPTT) within 7 days prior to Enrollment:
 - ≤1.5 x ULN (except for patients receiving anticoagulation therapy) in the absence of therapeutic intent to anti-coagulate the patient;

Version: Amendment 4 Date: 31 Mar 2020

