Abnormal values in AST and/or ALT concurrent with abnormal elevations in total bilirubin that meet the criteria outlined below in the absence of other causes of liver injury are considered potential cases of drug-induced liver injury (potential Hy's Law cases) and should always be considered important medical events.

The threshold of laboratory abnormalities for a potential case of drug-induced liver injury depends on the patient's individual baseline values and underlying conditions. Patients who present with the following laboratory abnormalities should be evaluated further to definitively determine the etiology of the abnormal laboratory values:

- Patients with AST or ALT and total bilirubin baseline values within the normal range who subsequently present with AST or ALT ≥ 3 x ULN concurrent with a total bilirubin ≥ 2 x ULN with no evidence of hemolysis and an alkaline phosphatase $\leq 2 \times \text{ULN}$ or not available;
- For patients with preexisting ALT OR AST OR total bilirubin values above the upper limit of normal, the following threshold values should be used in the definition mentioned above:
- For patients with pre-existing AST or ALT baseline values above the normal range: AST or ALT \geq 2 x the baseline values and \geq 3 x ULN, or \geq 8 x ULN (whichever is smaller);
- For patients with pre-existing values of total bilirubin above the normal range: Total bilirubin increased by one time the ULN $or \ge 3$ x the lower limit of normal (whichever is smaller).

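### The retreatment rule requires normal bilirubin although entry allows up to 1.5 x ULN, so an eligible patient with an unchanged mild elevation could be removed at about Day 42 without toxicity

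*Combined protocol and SAP*

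**What the plan says.** Inclusion criterion 10 (protocol section 4.2.1, repeated in the synopsis) sets the entry limit, measured within 14 days before Day 1: "Total bilirubin ≤ 1.5 x ULN".

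Section 4.9.1 lists the organ function that must be present before the next cycle, checked within 48 hours of its start. For bilirubin the requirement is "Total bilirubin within normal institutional limits". Two consequences follow in the same section: "Patients not fulfilling these criteria should have treatment delayed until the recovery of organ function", and "Patients who cannot be retreated within 2 weeks of the end of the previous cycle should be removed from study".

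Section 4.9.2 adds a discretionary route. Where the balance of risk and benefit supports continuing, "patients may continue with a reduced dose or a change of treatment schedule if the Investigator and medical monitor agree".

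Elsewhere the protocol does allow for raised baselines. The hepatic DLT rule in 3.7.1 counts only "elevations that do not return to ≤ Grade 1 (if normal at study entry) or ≤ baseline values within 7 days" of stopping drug. The same list has an entry that begins "For patients with Gilbert's disease and with Grade 2 bilirubin at baseline". The liver-injury rule in 5.5.1 has a separate threshold that begins "For patients with pre-existing values of total bilirubin above the normal range".

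**The concern.** The retreatment limit is stricter than the entry limit for the same test, and it is an absolute value with no reference to baseline. A patient can therefore be fit to receive 28 days of drug and, with the same laboratory value, be unfit for day 29. Under the literal rule that patient leaves treatment for a reason known at enrollment.

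In a small descriptive study such a discontinuation is costly for two reasons.

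- **No replacement.** Section 4.11.1 allows none in Stage 2, and section 4.3.1 limits Stage 1 replacement to withdrawals before the DLT period ends. Removal at about Day 42 falls after that period.
- **Thin tumor data.** The patient leaves before the first on-treatment 8-weekly MRI. Table 1 schedules an End of Treatment MRI but none in long-term follow-up, so unless extra scans are obtained, that may be the only post-baseline scan. With a single scan the patient cannot have the two consecutive assessments, at least 28 days apart, that section 6.3.4 requires for confirmed disease control (an exploratory endpoint). If that scan is missed or cannot be evaluated, the patient also falls outside the mITT population (6.3.1), which is the primary population for Stage 2 PFS (6.3.4).

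For the patient, it could mean losing study treatment without toxicity or progression.

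**Working it through.** The plan gives no figure to reproduce here. The check is a comparison of limits followed by day arithmetic.

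**Entry limits (4.2.1) against retreatment limits (4.9.1)**

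| Test | Entry | Before each later cycle | Same level? |
|---|---|---|---|
| Neutrophils | > 1,500/mm³ | ≥ 1.5 x 10⁹/L (= 1,500/mm³) | Yes |
| Platelets | > 100,000/mm³ | ≥ 100 x 10⁹/L (= 100,000/mm³) | Yes |
| AST/ALT | ≤ 2.5 x ULN | ≤ 2.5 x ULN | Yes |
| Total bilirubin | ≤ 1.5 x ULN | within normal, i.e. ≤ 1.0 x ULN | **No** |

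The band that is eligible at entry but fails retreatment is above 1.0 and up to 1.5 x ULN.

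**Timeline for a patient whose value stays in that band**

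- Cycle length is 28 days (4.7), so Cycle 1 ends on Day 28.
- The longest delay is 2 weeks = 14 days (4.9.1).
- Removal: 28 + 14 = Day 42. This is approximate, since the Cycle 2 Day 1 visit has a window of +/- 3 days.
- First scheduled on-treatment MRI: Week 8 (4.6.3) = 8 x 7 = Day 56. With the +/- 3-day window in Table 1, the earliest date is 56 - 3 = Day 53.
- Gap between removal and scan: 56 - 42 = 14 days, or 53 - 42 = 11 days at the earliest.
- On-treatment 8-weekly MRIs done by Day 42: 0.

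**What such a patient still contributes**

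- The Cycle 1 DLT assessment, because its window closes on Day 28.
- The Cycle 1 Day 1 PK profile and, if it is drawn, the Cycle 2 Day 1 pre-dose sample, which is read against the recorded time of the Day 28 dose (4.6.7).
- The End of Treatment MRI (Table 1).
- Follow-up every 8 weeks for progression and death (4.8). Evaluable tumor data count until new anti-cancer therapy starts (6.3.4).

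**What is lost:** exposure and tolerability data beyond Cycle 1, and the on-treatment 8-weekly scans.

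**With the proposed change:** the band closes for patients who were raised at entry. An unchanged value would let Cycle 2 start on schedule, with no removal at Day 42.

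**The case against.** The strongest reply has five parts.

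1. **Wording.** Section 4.9.1 speaks of recovery, which presupposes a loss, and a patient still at the accepted entry value has lost nothing. Both the delay and the removal are phrased as recommendations. A sensible site might simply continue. This leaves room for a softer reading, but the text does not state one. The listed criteria are absolute values, and the hold covers everyone who fails them. Sites could also resolve the matter differently from one another.
2. **Discretion.** Section 4.9.2 is not limited to patients with an adverse event, which is given there only as an example, so removal is not the only outcome foreseen. That is true. However, it offers only a lower dose or a changed schedule. It does not waive the laboratory limit, and a patient without toxicity needs neither remedy.
3. **Deliberate caution.** A tighter liver limit can be a conservative safety choice, and DLT or liver-injury thresholds serve a different purpose from retreatment thresholds. That is fair. Those clauses show only that raised baselines were foreseen, and the Gilbert's line is used for no more than that, since its Grade 2 level need not fall inside the entry limit. But caution does not explain why treatment may start at a value that bars its continuation, and the documents give no reason.
4. **Size.** The number of affected patients is unknown and may be zero in a study of about 32. The primary endpoint is untouched, and an evaluable End of Treatment scan keeps the patient in mITT. All of this stands and limits the weight of the point.
5. **The remedy.** A patient normal at entry who reaches 1.1 x ULN would be held, while one who entered at 1.1 and rises to 1.5 would continue. This asymmetry is real, but it stays within a level the protocol already accepts for dosing.

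**Conclusion.** The concern holds. The entry and retreatment limits for total bilirubin conflict, and followed as written the rule takes an eligible patient with a stable mild elevation off study at about Day 42 for a reason unrelated to drug or disease.

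The size can be stated only per affected patient: 28 days of dosing, a hold of up to 14 days, and no on-treatment 8-weekly MRI. The conclusion assumes that:

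- the patient enters above 1.0 and up to 1.5 x ULN;
- every repeat value during the 2-week hold stays above normal; and
- the site applies 4.9.1 literally.

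How many patients would meet these conditions cannot be derived from the documents. The point does not threaten the DLT endpoint. It should be fixed because the stated rule gives a wrong result and the correction is small.

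**What to change.** Keep the bilirubin bullet in 4.9.1 and add a clause after it: *or, if above normal at entry, ≤ 1.5 x ULN (the entry limit)*.

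This retains the stricter hold for patients who were normal at entry and brings the rule for the others into line with inclusion criterion 10. The downside is that a patient raised at entry could be retreated after a small further rise, as long as the value stays within the entry limit.

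The cost is one bullet at the next amendment, with no new procedure, visit or data.
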